#### **9.2.4 Per-Protocol Analysis Set (PPS)**

The PPS analysis set excludes subjects from the FAS population due to major protocol deviations with potential to substantively affect the results of the primary efficacy analysis. The PPS population will be used for a sensitivity analysis for primary and key secondary efficacy endpoints.

Determination of the major protocol deviations will be made prior to unblinding of the database and documented in a separate report.

### **9.3 Primary Estimand, Intercurrent Events, and Estimation**

**Primary Objective and Population:** The primary objective is to compare the efficacy of intranasal administration of twice-daily doses of 186 and 372 µg of OPN-375 (fluticasone propionate) with placebo in subjects with documented CRS with or without nasal polyps.

#### **9.3.1 Co-primary Endpoints**

- Change from baseline to the end of Week 4 in 7-day average instantaneous AM CSNS (evaluation of symptom severity immediately preceding the time of scoring):
  - nasal congestion
  - nasal discharge (anterior and/or posterior)
  - facial pain or pressure sensation

The baseline CSNS will be the average of the CSNS over the last 7 days of the placebo run-in period prior to randomization. The CSNS at Week 4 will be the average of the CSNS over the 7 days prior to nominal Study Day 28.

AND

- Change from baseline to Week 24/ET in the APOV in the ethmoid and maxillary sinuses (APOV is the average percentage of volume opacified across both maxillary and ethmoid sinuses (all 4 sinuses) at each time point)

#### **9.3.2 Potential Intercurrent Events**

The potential intercurrent events are as follows:

1. Need for systemic corticosteroids for CRS exacerbation or worsening of CRS nasal/sinus symptoms
2. Need for nasal surgery
3. Discontinuation from study treatment

#### **9.3.3 Primary Estimand**

The primary efficacy estimand is the difference between each active treatment of twice-daily doses of 186 µg and 372 µg of OPN-375 and placebo for each of the co-primary endpoints.

For the primary estimand, intercurrent events will be addressed as follows:

1. Systemic corticosteroids use for CRS exacerbation or worsening of CRS nasal/sinus symptoms: a composite strategy will be employed with a poor score assigned to this event.
  - For CSNS, a value of '9' will be assigned. For APOV, a poor score is defined as follows: for a subject with a baseline APOV  $\geq 75\%$ , a value of '100%' is assigned; if baseline APOV  $< 75\%$ , a poor score is defined as baseline APOV + 25%. The rationale for assignment of a poor score is provided in the SAP. Also, further detail regarding the handling of a missing within-instrument data in these endpoints is provided in the SAP.
  - Systemic corticosteroid use for other indications will be considered a treatment and study discontinuation event (reference criteria 3).
2. Nasal surgery: composite strategy with poor scores assigned as above.
3. Treatment Discontinuation: treatment policy strategy; subjects may continue in the study until one of the following three mutually exclusive outcomes:
  - a. Subject completes Week 24/ET CT scan. In the absence of an intercurrent event (systemic corticosteroids, nasal surgery) use the endpoint value;
  - b. An intercurrent event (systemic corticosteroids for CRS exacerbation or worsening of CRS nasal/sinus symptoms, nasal surgery) occurs: Use composite strategy and assign poor score as described above (reference criteria 1,2);
  - c. Subject discontinues the study. Missing data due to study discontinuation following treatment discontinuation will be imputed; further detail on the imputation method is provided in the estimation section for each of the co-primary endpoints.

#### 9.3.4 Estimator and Estimation Method - Primary Analysis

Estimator and estimation method (CSNS): For the co-primary endpoint CSNS, the estimator is the mean difference between treatments (active versus placebo) in change from baseline to the end of Week 4 in the 7-day average total instantaneous AM CSNS. Estimation is based on a mixed model for repeated measures (MMRM) where changes from baseline to Weeks 2, 4 in the 7-day average total instantaneous AM CSNS, respectively, are the repeated measures. The MMRM model will employ Restricted Maximum Likelihood (REML) for parameter estimation and the Kenward-Roger method for calculating the denominator degrees of freedom. An unstructured covariance matrix will be used to estimate within-subject error. For the treatment policy estimand, (reference [Section 9.3.3](#), criteria 3c), missing data due to study discontinuation will be estimated within the MMRM model under the assumption that the missing data are missing at random (MAR) and that early discontinuation from the study (prior to Week 4) is unlikely to reflect a treatment effect.

The MMRM model will include categorical effects for previous sinus surgery (Y, N), nasal polyp status (present, absent), treatment (OPN-375 186  $\mu$ g, OPN-375 372  $\mu$ g, placebo), week (2, 4), treatment-by-day interaction, and the continuous covariate baseline 7-day average total instantaneous AM CSNS with baseline-by-week interaction.

**Estimator and estimation method (APOV):** For the co-primary endpoint APOV, the estimator is the mean difference between treatments (active versus placebo) in the change from baseline to Week 24/ET APOV. Estimation is based on an ANCOVA model including categorical effects for previous sinus surgery (Y, N), nasal polyp status (present, absent), treatment (OPN-375 186 µg, OPN-375 372 µg, placebo), and baseline APOV.

For the treatment policy estimand, (reference Section 9.3.3, criteria 3,c), missing data due to study discontinuation will be imputed with a pattern mixture model (PMM) multiple imputation (MI) using the Jump-to-Control (J2C) method. The PMM assumes that the missing data at Week 24/ET on the control arm (placebo) is MAR, and the missing data on the active treatment arms have the profile of the control arm at Week 24/ET.

Multiple imputation using a PMM with J2C method will be conducted using the sequential modeling method as described in ([O'Kelly et al, 2014](#)). Further detail on the MI implementation, and statistical analysis and inference is provided in the SAP.

### 9.3.5 Supplementary Analysis

A supplementary analysis of the primary estimand will be performed.

**Supplementary estimand:** A supplementary efficacy estimand is the difference between each active treatment of twice-daily doses of 186 µg and 372 µg of OPN-375 and placebo in each of the co-primary endpoints, irrespective of systemic corticosteroid use.

That is, for the supplemental estimand, intercurrent events will be addressed as follows:

1. Systemic corticosteroids use for all indications: treatment policy strategy; consider outcomes irrespective of systemic corticosteroid use; subjects may continue in the study until one of the following two mutually exclusive outcomes:
  - a. Subject completes the study, use the endpoint value;
  - b. Subject discontinues the study. Missing data due to study discontinuation following treatment discontinuation will be imputed; further detail on the imputation method is provided in the estimation section for each of the co-primary endpoints.
2. Nasal surgery: composite strategy with poor scores assigned.
3. Treatment discontinuation: composite strategy with poor scores assigned.

The estimator and estimation methods for the co-primary endpoints, as well as the assignment of poor scores, are the same as for the primary estimand described above.

## 9.4 Sensitivity Analyses

### 9.4.1 ANCOVA on Ranked APOV Values

A sensitivity analysis of the primary estimand and APOV co-primary endpoint will be performed based on ranked APOV values after modification of the primary estimand as follows. For the composite strategy, a worst score of 100% is assigned; for the treatment policy strategy, baseline APOV is assigned (BOCF). Baseline and endpoint APOV values are then ranked. Ranked APOV values will be analyzed with an ANCOVA model including categorical effects for previous sinus surgery and treatment. The method described by Koch, et. al. (1982) using extended Mantel-Haenszel statistics will be used to perform nonparametric treatment comparisons, adjusting for

the baseline covariate. Implementation of this method is described in Stokes, et. al., Chapter 7 (2012).

#### 9.4.2 Tipping Point Analysis

If the analysis of both co-primary endpoints is statistically significant, then an additional sensitivity analysis will be performed to determine the smallest constant,  $\delta$ , when applied to the imputed missing data in the active treatment groups, that will yield a mean treatment difference such that the result using the primary analysis model is no longer statistically significant. The constant  $\delta$  represents a worsening of treatment values and the smallest value, say  $\delta^*$ , that yields a non-significant result for the primary analysis is called the “Tipping Point.” Further detail on the Tipping Point analysis is provided in the SAP.

### 9.5 Key Secondary Efficacy Analyses - Pooling of Study 3205 and Study 3206

The following analyses are based on the key secondary endpoints which are defined by pooling the data from Study OPN-FLU-CS-3205 and Study OPN-FLU-CS-3206; further details are provided in the SAP:

- Change from baseline to Week 4 on CSNS score in subjects who were symptomatic at trial entry despite reported use of an intranasal steroid for treatment of CRS within 30 days of Visit 1 will be analyzed using the same MMRM model described for the co-primary endpoint CSNS and the model will include a categorical effect term for protocol (CS-3205, CS-3206).
- The frequency of acute sinus exacerbations over 24 weeks will be compared between OPN-375 dose groups and placebo using generalized linear model (GLM) for data from the negative binomial distribution that is commonly referred to as the negative binomial (NB) regression model. The NB model will include the same model terms as the primary models; in addition, the model will include a categorical effect for protocol (CS-3205, CS-3206), and the logarithm of follow-up time as an offset variable.

### 9.6 Other Secondary Efficacy Analyses

All statistical analyses in this section that reference the primary MMRM and ANCOVA models described in Section 9.3.4 will include the same factors as their respective primary models, except for the baseline covariate. The baseline covariate for the specific endpoint will be used, unless otherwise specified.

In addition, a combined dose group (OPN-375 186  $\mu$ g, OPN-375 372  $\mu$ g) is defined in all models of primary and secondary endpoints by including appropriate model contrasts, assigning equal weight to each dose, to obtain the inferential statistics for combined doses, and for the comparison: combined dose versus placebo.

Intercurrent events for secondary endpoints will be addressed as described in Section 9.3.3 for the primary estimand, unless otherwise indicated, and poor scores assigned to secondary endpoints are defined in the SAP. For the treatment policy estimand, missing data due to study discontinuation will be handled as described in Section 9.3.4 for the primary MMRM and ANCOVA models, respectively.

The following secondary endpoints will be analyzed with MMRM models; further details will be provided in the SAP:

- Changes from baseline in average instantaneous and reflective AM and PM CSNS and symptom scores (facial pain or pressure sensation, nasal discharge, and nasal congestion)
- Change from baseline SNOT-22 total scores and sub-domain scores
- Change from baseline to Week 24/ET in SNOT-22 total score in subjects from pooling studies OPN-FLU-CS-3205 and OPN-FLU-CS-3206 who report using an intranasal, topically acting nasal steroid for the treatment of CRS within 30 days of Visit 1
- Change from baseline PSQI global and component scores
- Change from baseline to Week 24/ET the Global PSQI Score from pooling studies OPN-FLU-CS-3205 and OPN-FLU-CS-3206
- Change from baseline to Week 4, 8, 12, and 24/ET in HPQ endpoints
  - number and percentage of missing work days over the past 4 weeks
  - percentage of productive work hours lost over the past 4 weeks

The following secondary endpoints will be analyzed using an ANCOVA model; further details will be provided in the SAP. Change from baseline to Week 24/ET:

- Lund-Mackay Staging System total score, scores for ethmoids and maxillary sinuses combined, and scores for each sinus pair (e.g., ethmoids, maxillary, frontal, sphenoid, and ostiomeatal complex),
- WPOV-E, WPOV-M, WPOV
- Zinreich modification of the Lund-Mackay Staging System total score, scores for ethmoids and maxillary sinuses combined, and for each sinus pair (e.g., ethmoids, maxillary, frontal, and sphenoid)
- Zinreich modification of the Lund-Mackay Staging System score for the worst sinus between maxillary and ethmoid sinuses
- SF36v2 MCS Domain, PCS Domain, and individual health domains
- QIDS total score
- SIT scores

Change from baseline to Week 24/ET for EQ-5D VAS scores will be analyzed with the ANCOVA model described above; EQ-5D dimensions will be summarized. Further details will be provided in the SAP.

The percent of subjects considered improved (ie, subjects with ratings of 1 [very much improved] or 2 [much improved]) based on the PGIC at weeks 4 and 24/ET will be analyzed with a logistic regression MMRM model; further details will be provided in the SAP.

The Kaplan-Meier method and log-rank test will be used to estimate and compare the distributions of time to first exacerbation between OPN-375 and placebo.

The following endpoints will be analyzed using a logistic regression model; further details will be provided in the SAP:

- QIDS Severity of Depression at Week 24/ET
- The percent of subjects requiring rescue medication from Week 4 to Week 12; subjects without use of any rescue medication during the period Week 4 to Week 12 will be referred to as rescue-free subjects.
- The percentage of subjects who meet the eligibility criteria for surgery at Week 24

The percent of subjects indicating that they are willing to consider sinus surgery at baseline and Week 24, and the percent of subjects approved for surgery who no longer elect to undergo a surgery Week 24 within each treatment group will be compared with McNemar's test.

The total number of times a subject requires rescue medication after Week 4 to Week 12 will be tabulated. Rescue free subjects will be assigned a zero ('0') for this tabulation. This endpoint will be analyzed with an ANCOVA model based on ranks.

Change from baseline to Week 24/ET for SF-6D will be summarized as described in the SAP.

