7.5.2 SNOT-22 Total Score and Domain Scores

The SNOT-22 instrument is described in Section 9.3.3. For SNOT-22 total score, a poor score is defined as follows: for a subject with a baseline SNOT-22 total score ≥ 92 , a value of '110' is assigned; if baseline SNOT-22 total score < 92 , a poor score is defined as baseline SNOT-22 total score + 18 for the composite strategy, per the primary estimand. For the individual Domain SNOT-22 scores, the worst value for the respective domain (Table 9.4) will be applied.

Changes from baseline to Weeks 4, 8, 12 and 24/ET in SNOT-22 total scores and each of the 5 Domain scores will be analyzed using the MMRM model described in Section 7.1.5 where the repeated measures include change from baseline in SNOT-22 total scores at Week 4, 8, 12, and 24/ET. The model-based LS mean difference between each active treatment group and placebo (active-placebo), 95% CI, and nominal p-value will be displayed for each analysis time point.

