7.5.3.1 Average Percentage of Opacified Volume in the Individual Sinuses

Change from baseline in APOV-E and APOV-M will be analyzed with the ANCOVA model described in Section 7.1.5. A poor score is assigned as defined in Section 7.1.3 for the APOV co-primary endpoint. The model-based LS mean difference between each active treatment group and placebo (active-placebo), 95% CI, and nominal p-value will be displayed.

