7.5.4 Qualitative CT Scan Assessment

The protocol for qualitative CT scan imaging assessments is based on the Image Review Charter (IRC) – Revision C, (29 January 2020). Qualitative CT scan assessments will be performed at baseline and Week 24/ET in accordance with the IRC for Lund-Mackay Staging (LM) and Zinreich Modification of the Lund-Mackay Staging (ZLM). Further detail on LM and ZLM image scoring metrics and adjudication procedure, and the definitions of the analysis variables derived from these scoring metrics is provided in Section 9.3.6.

For LM total score, a poor score is defined as follows: for a subject with a baseline LM total score ≥ 18 , a value of '24' is assigned; if baseline LM total score < 18 , a poor score is defined as baseline LM total score + 6 for the composite strategy, per the primary estimand.

For ZLM total score, a poor score is defined as follows: for a subject with a baseline ZLM total score ≥ 39 , a value of '50' is assigned; if baseline ZLM total score < 39 , a poor score is defined as baseline ZLM total score + 11 for the composite strategy, per the primary estimand.

Other LM and ZLM efficacy endpoints will be assigned scores for the composite strategy, per the primary estimand, as listed in Table 7.1.

Table 7.1
Worst Score Assignment for LM and ZLM efficacy variables

Efficacy Variable	LM worst score	ZLM worst score
Ethmoid + Maxillary	12	30
Sinus Pair	4	10

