7.5.5 PSQI Global and Component Scores

The Pittsburgh Sleep Quality Index (PSQI) is a validated, self-rated questionnaire, which assesses sleep quality and disturbances over a 1-month time interval; further details on the PSQI instrument are provided in Section 9.3.7. PSQI is measured at baseline, Week 12, and Week 24/ET. For PSQI Global score, a poor score is defined as follows: for a subject with a baseline PSQI Global score ≥ 17 , a value of ‘21’ is assigned; if baseline PSQI Global score < 17 , a poor score is defined as baseline PSQI Global score + 4 for the composite strategy, per the primary estimand. For PSQI component scores, the worst score for the component will be assigned.

Changes from baseline to Week 12 and Week 24/ET in PSQI Global score and component scores (reference Appendix, Section 13.1) will be analyzed using the MMRM model described in Section 7.1.5, where the repeated measures include change from baseline scores at Week 12 and 24/ET. The model-based LS mean difference between each active treatment group and placebo (active-placebo), 95% CI, and nominal p-value will be displayed for each analysis time point.

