9.3.3 SNOT-22 Total and Domain Scores

SNOT-22 is a subject-completed questionnaire that consists of 22 symptoms and social/emotional consequences of their nasal disorder. Each item is rated as follows: 0=no problem, 1=very mild problem, 2=mild or slight problem, 3=moderate problem, 4=severe problem, 5=problem as bad as it can be. The SNOT-22 is validated in CRS ([Hopkins 2009](#)). The recall period is the past 2 weeks.

Five domain scores will be derived from the SNOT-22 for efficacy evaluation (Table 9.4): Rhinologic Symptoms; Extra-Nasal Rhinologic symptoms, Ear and Facial Symptoms; Sleep Function; Psychological Issues; and the total score (sum of all items).

Table 9.4: SNOT-22 Domain and Total Scores

Domain	Sum of Items	Range
Rhinologic Symptoms	1, 2, 3, 6, 21, 22	0-30
Extra-Nasal Rhinologic Symptoms	4, 5, 6	0-15
Ear/Facial Symptoms	2, 7, 8, 9, 10	0-25
Psychological Dysfunction	14, 15, 16, 17, 18, 19, 20	0-35
Sleep Dysfunction	11, 12, 13, 14, 15	0-25
TOTAL SCORE	Sum of all 22 items	0-110

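### After a steroid or surgery event the SAP moves totals a modest step from baseline but sets their parts to the scale extreme, so the two cannot belong to the same subject

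*Protocol*

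**What the plan says.** Protocol 9.6 carries the primary estimand's handling of intercurrent events over to the secondary endpoints and adds that "poor scores assigned to secondary endpoints are defined in the SAP". The composite strategy covers two events, systemic steroids taken for CRS and nasal surgery (SAP 7.1.3). A subject with either is called a failure below.

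- **SNOT-22 (SAP 7.5.2).** Total: "a poor score is defined as baseline SNOT-22 total score + 18 for the composite strategy, per the primary estimand", or 110 from a baseline of 92 upwards. Domains: "For the individual Domain SNOT-22 scores, the worst value for the respective domain (Table 9.4) will be applied".
- **PSQI (SAP 7.5.5).** Global score: baseline + 4, or 21 from a baseline of 17 upwards. Components: "For PSQI component scores, the worst score for the component will be assigned".
- **LM and ZLM (SAP 7.5.4).** LM total: baseline + 6, or 24 from 18 upwards. ZLM total: "if baseline ZLM total score < 39 , a poor score is defined as baseline ZLM total score + 11", or 50 from 39 upwards. Table 7.1, titled "Worst Score Assignment for LM and ZLM efficacy variables", gives 12 (LM) and 30 (ZLM) to the ethmoid-plus-maxillary score, and 4 and 10 to each sinus pair. These are the maxima in SAP 9.3.6.
- **SF-36v2 (SAP 7.5.6, 7.5.7).** MCS: baseline − 18. PCS: baseline − 11. Neither goes below 0. Each individual domain: 0. SAP 9.3.4 says that t-scores are what both sections analyse.

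SAP 7.1.4 explains why poor scores are used at all. A worst score ties the change to the baseline, can yield changes not seen in practice, and lets a few subjects move the estimate, so the section advises against it. It bases the poor score on the 97.5th percentile of observed change scores. The SAP gives no reason for keeping worst scores on the parts.

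**The concern.** These totals are built from the parts. SAP 9.3.3 defines the SNOT-22 total as "Sum of all 22 items", PSQI global is the sum of seven components (SAP 9.3.7), and the ZLM and LM totals are sums of 10 and 12 site scores (SAP 9.3.6). A rule that moves a total by a small step and its parts to the ceiling describes a subject who cannot exist.

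The parts are listed secondary endpoints, reported with LS mean differences, confidence intervals and nominal p-values. SNOT-22 domains are also analysed by polyp and surgery subgroup (SAP 7.8.3). A reader who compares a total with its domains could take a difference made by the scoring rule for a clinical pattern. The unrealistic change scores that SAP 7.1.4 set out to avoid also return at the level of the parts.

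**Working it through.** **1. The plan's own cut-offs.** Cut-off = scale maximum − step: SNOT-22 110 − 18 = 92; PSQI 21 − 4 = 17; LM 24 − 6 = 18; ZLM 50 − 11 = 39. All four reproduce.

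**2. What the assigned parts imply for the total.**
- SNOT-22: the five domains in Table 9.4 cover all 22 items, so every domain at its maximum puts every item at 5: 22 × 5 = 110.
- PSQI: 7 × 3 = 21.
- ZLM: 5 pairs × 10 = 50.
- LM: 5 sinus pairs × 4 = 20, or 24 if the ostiomeatal pair also gets 4. SAP 3.4.3 lists that complex among the pairs, while SAP 9.3.6 defines pair scores for five sinuses. The five sinus pairs alone exceed the assigned total when baseline + 6 < 20, that is, below a baseline of 14.

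**3. Change per failure.** Ratio = (maximum − baseline) / step. The documents give no baseline means, so the baselines are illustrative.

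| Scale | Baseline | Assigned total | Total implied by parts | Ratio |
|---|---|---|---|---|
| SNOT-22 | 45 | 63 | 110 | 65/18 = 3.6 |
| PSQI | 9 | 13 | 21 | 12/4 = 3.0 |
| LM | 12 | 18 | 24 | 12/6 = 2.0 |
| ZLM | 25 | 36 | 50 | 25/11 = 2.3 |

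The LM row assumes that the ostiomeatal pair gets 4. The ratio is 2 to 4 for baselines from 74 down to 38 (SNOT-22), 13 to 5 (PSQI), 12 to 0 (LM) and 28 to 6 (ZLM). It is 1.0 at the cut-offs. At 20% of scale it is 4.9, 4.2, 3.2 and 3.6.

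A part can also worsen more than its whole. A ZLM ethmoid-plus-maxillary score going from 17 to 30 rises 13, while the total rises 11.

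SF-36v2 domains are not simple addends of MCS or PCS, so the comparison is only indicative. From a t-score of 50, a drop to 0 is 50/18 = 2.8 times the MCS step and 50/11 = 4.5 times the PCS step.

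**4. Between-arm effect.** With q the failure share, m the mean change in non-failures and J the change assigned to a failure, for active (a) and placebo (p):

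D = [(1 − q_a)m_a + q_a J] − [(1 − q_p)m_p + q_p J]

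Take the 0–30 SNOT-22 domain at baseline 15. The worst score gives J = 15. A step in proportion to the total's gives J = 30 × 18/110 = 4.9. Assume m_a = −8 and m_p = −5.

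| Failures, active / placebo | D before the J term | D, J = 4.9 | D, J = 15 |
|---|---|---|---|
| 10% / 10% | −7.20 + 4.50 = −2.70 | −2.70 | −2.70 |
| 5% / 15% | −7.60 + 4.25 = −3.35, then −0.10 J | −3.84 | −4.85 |
| 15% / 5% | −6.80 + 4.75 = −2.05, then +0.10 J | −1.56 | −0.55 |

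The worst-score rule multiplies D by 1.00, by 4.85/3.84 = 1.26, and by 0.55/1.56 = 0.35.

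Over domain baselines of 12, 15 and 18, with failures at 5%/10%, 5%/15% and 2%/20%, the multiplier is about 1.1 to 1.9 when non-failures differ between arms by 1 to 3 points. It is 1.7 to 3.7 only when non-failures do not differ at all.

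**5. Precision with equal rates.** Within-arm variance = (1 − q)s² + q(1 − q)(J − m)², with an assumed s = 6, q = 10% and 111 per arm. For J = 4.9 the two arms give 47.4 and 41.2, so z = 2.70/√(88.6/111) = 3.02. For J = 15 they give 80.0 and 68.4, so z = 2.70/√(148.4/111) = 2.34.

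**The case against.** Five points can be made for the plan.

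- **Protocol 9.6 is not breached.** A reader might infer a breach, because the SAP labels the part values as worst scores. Protocol 9.3.3 itself counts a CSNS of 9, the scale maximum, as a poor score, so a maximum falls within the protocol's term. The conflict is with the reasoning of SAP 7.1.4. This stands.
- **Not every total is affected.** CSNS at 9 agrees with its three symptoms at 3 each (3 + 3 + 3 = 9, SAP 9.3.1). This stands.
- **The volumetric endpoints are not a perfect model.** For APOV-E and APOV-M the SAP says "A poor score is assigned as defined in Section 7.1.3 for the APOV co-primary endpoint", which keeps whole and parts on one scale. Exact agreement still fails after capping: with APOV-E 90 and APOV-M 50, APOV is 70 and becomes 95, while the parts become 100 and 75, mean 87.5. Likewise, an ethmoid that is the worst sinus at 50% becomes 79% as WPOV and 83% as WPOV-E. This stands, though these gaps come from capping or from endpoint-specific percentiles, not from mixing two kinds of score.
- **No error-controlled result moves.** The co-primary and key secondary tests do not use these parts, and SAP 7 gives other endpoints nominal p-values. This stands and limits the weight of the point.
- **A separate SAP Addendum of 26 October 2021 documents the poor scores.** It is not among the documents reviewed and may defend maxima on short scales or contain part-level percentiles. The SAP body nevertheless states the maxima outright and gives no reason. If the Addendum holds part-level steps, the two need reconciling.

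**Conclusion.** The inconsistency is real for SNOT-22, PSQI, LM and ZLM below baselines of 92, 17, 18 and 39. The LM figure assumes the ostiomeatal pair is scored like the others; without that, the conflict is certain only below 14. SF-36v2 has the same pattern in the other direction, with the added question of what 0 means when t-scores are analysed.

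The factor of 2 to 4 applies to one failure's assigned change at assumed mid-range baselines. A reader might infer that treatment effects on the parts are inflated 2 to 4 times. The documents do not support that, because they give neither failure rates by arm nor changes in non-failures. With equal rates the estimate does not move but loses precision. With fewer failures on active it grows, and with more it shrinks. The rule can therefore exaggerate or mask a domain effect. The point merits correction, but it does not bear on the trial's formal conclusions.

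**What to change.** In SAP 7.5.2, 7.5.4 (Table 7.1), 7.5.5 and 7.5.7, assign each part a capped baseline-plus-increment poor score, or baseline-minus for SF-36v2 domains on the t-score metric. Take the increment from the blinded 97.5th percentile of change for that part, the method of SAP 7.1.4.

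If no percentile was derived for the SNOT-22, PSQI, LM or ZLM parts, use the total's step in proportion to the part's range:

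- ZLM pair 10 × 11/50 = 2.2; ZLM ethmoid-plus-maxillary 30 × 11/50 = 6.6
- LM pair 4 × 6/24 = 1; LM ethmoid-plus-maxillary 12 × 6/24 = 3
- PSQI component 3 × 4/21 = 0.57
- SNOT-22 domain 18 × range/110

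This fallback does not suit SF-36v2, whose domains are not addends of the summaries. State also whether the ostiomeatal pair falls under Table 7.1. Keep the worst-score version as a sensitivity analysis.

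The cost is SAP wording and a programming change, settled before unblinding. Part-level differences driven by failures become smaller. Totals and parts come onto a comparable scale, but exact additivity is not guaranteed. ZLM pairs of 10, 8, 3, 2 and 2 (total 25), each raised by 2.2 and capped, sum to 10 + 10 + 5.2 + 4.2 + 4.2 = 33.6, not 36. Because SNOT-22 domains share items, their steps sum to 130 × 18/110 = 21.3, not 18.
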